Wound Assessment			x	X				X
Pain Assessments ³	X	X	X	X	X	x	X	X
Quality of Life Questionnaires ⁴	X			Х	X	х	х	X
Daily Pain Medication Diary and Concomitant Medication Log ⁵	х	Х	х	х	Х	Х	х	х
Daily Pain Diary	X	X	X	X	X	X	X	X
Adverse Events		X	х	x	X	X	x	X
	nstances. Visit 1 and							

^{*}Note: In some instances, Visit 1 and Visit 2 can occur on the same day.

Vital signs to include weight, seated systolic/diastolic BP measured in millimeters of mercury (mm Hg), HR (beats per minute), respiration rate (breaths Vital signs to include weight, seated systolic/diastolic BP measured in millimeters of mercury (mm Hg), HR (beats per minute), respiration rate (breaths per minute), and temperature in degrees Celsius (°C). Obtain at the beginning of each visit before any additional assessments are completed. Height will only be recorded one time at visit 1

2 Comparative study only

3 Pain Assessments: VAS and PROMIS® (for V2 Operative Day 0, VAS and PROMIS® performed prior to nerve block, nerve block oNLY if nerve block is performed during screening visit).

4 Quality of Life Questionnaires include: FHSQ

Beile Provided the Provided Provide

^{5.} Daily Pain Medication Diary (including quantity, quality and class of pain medications) related to the nerve injury should be collected during Screening and Operative day and any changes/additions should be collected during the study.

6. Definitions and Terminology

Baseline

Baseline may be considered to be Day 0 (day of the procedure) or the screening period prior to Day 0 depending on appropriateness for the analysis.

Baseline Value

For purposes of analysis, the baseline value is defined as the value captured at the baseline assessment. If this value is not available, the most recent value obtained prior to the repair will be used for the baseline value.

Change from Baseline

Change from baseline will be calculated as post-baseline value – baseline value, unless otherwise noted.

Study Day

Study Day is defined relative to Day 0: Study Day = event date - date of Day 0.

Days on Study

Days on Study is the number of days from Day 0 to the date of study completion or early termination.

Completed Subjects

The treatment period is defined as the time period during which subjects are expected to be evaluated post implantation up to 12 months. Subjects who are evaluated at the last scheduled visit determined by the investigator at each site for each patient will be defined as study completers.

Lost to Follow-Up

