For subjects who have not completed the study, who cannot be contacted, and who do not have a known reason for discontinuation (e.g., withdrew consent or adverse event, etc.), the reason for discontinuation will be "lost to follow-up".

Subject Non-Compliance

A subject is considered noncompliant if they fail to return for follow-up.

The Visual Analog or Analogue Scale for Pain

This pain scale is designed to present to the respondent a rating scale with minimum constraints. Respondents will mark the location on the 100-millimeter line corresponding to the amount of pain they experienced. VAS data are recorded as the number of millimeters from the left of the line with the range 0-100.

Patient Reported Outcome Measurement Information System Questionnaires

The PROMIS questionnaire is a set of person-centered measures that evaluates and monitors physical, mental, and social health in adults and children. Measures are applicable to the general

population and to those with chronic conditions. For this study, PROMIS measures will be used to monitor a subject's physical health/pain. The following six scales will be measured¹:

- Physical function
- Pain intensity
- Pain interference
- Fatigue
- Sleep disturbance
- Pain behavior

For each scale, raw scores are calculated by summing each individual question score. Raw scores are converted to a standard score with a mean of 50 and standard deviation of 10. The score is not valid if any items are missing. Conversion tables are listed in Appendix B.

Foot Health Status Questionnaire

The FHSQ was developed to help better measure responsiveness in overall foot health status. Four scales will be measured²:

- Foot Function
- General Foot Health
- Footwear
- Foot Pain

Each scale has a score ranging from 0 to 100, with higher scores representing better foot health and quality of life. When fewer than 50% of responses for any one scale are missing, any missing values for that scale are assigned to the average value of the non-missing questions.

Scoring will be calculated by transforming the raw scores for each sub-domain into an easily interpretable 0-100 scale, with 0 indicating poorest foot health and 100 representing no problems. The following formula was used to convert the raw scores for each sub-domain:

$$X = \left(\frac{X_{raw} - X_{worst}}{X_{optimal} - X_{worst}}\right) \times S_{optimal}$$

where,

 X_{raw} = Total score of the sub-domain

 X_{worst} = Score of the poorest state of foot health

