 $X_{optimal}$ = Score of the optimal foot health

 $S_{optimal}$ = Highest score of the new scale

Foot Function:

 $X_{worst} = 20$

 $X_{optimal} = 4$

 $S_{optimal} = 100$

Foot Health:

 $X_{\text{worst}} = 10$

 $X_{\text{optimal}} = 2$

 $S_{\text{optimal}} = 100$

Footwear:

 $X_{\text{worst}} = 3$

 $X_{\text{optimal}} = 15$

[figure not shown]
 $S_{\text{optimal}} = 100$

Foot Pain:

 $X_{\text{worst}} = 20$

 $X_{\text{optimal}} = 4$

 $S_{\text{optimal}} = 100$

Daily Pain Diary

A daily pain diary will be provided to each subject at the Screening visit (V1) and a new diary will be dispensed to the subject at Visits 2 through 7 to track incidence, frequency, and severity of pain (using a 10-point scale) daily. The diary will be reviewed and collected at each study visit (by the site team with the subject) prior to completing the scheduled pain assessments (VAS/PROMIS). The diary will also help track the use of subject pain medicine administration by reminding the subject to complete the Daily Pain Medication Diary for any pain medication/treatment taken by the subject at the time of the foot pain.

Daily Pain Medication Diary

A Daily Pain Medication Diary will be provided to each subject to take home and complete each day and will be reviewed at all visits. The subject will present the medication diary at each study visit for review by the site team and a new diary will be dispensed to the subject at each visit. The diary will be used to summarize pain medications by any use.

Opioid pain medications taken will be converted to morphine milligram equivalent (MME) where such conversions are available to summarize pain medications by quantity of use. For opioid and non-opioid pain medications, the Medication Quantification Scale⁴ (MQS) conversion will be used to convert medications to a comparable score. The MQS is a broader approach to quantifying medication consumption that captures non-opioid classes of medications without an equivalency to morphine. Unlike MME, two factors (detriment weight and dosage level) multiplied together scale the medication to a single score. Additionally, drugs will be categorized according to type of medication and the quantity taken will be summarized.

Recurrence of Symptomatic Neuroma

Subjects will be assessed for recurrence of symptomatic neuroma at the 3, 6, 9, and, 12 Month visits. The assessment intervals for each visit are as follows:

- Month 3 Visit: 6 Weeks after Operative Day 0 until Month 3 Visit

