- Month 6 Visit: Month 3 Visit until Month 6 Visit
- Month 9 Visit: Month 6 Visit until Month 9 Visit
- Month 12 Visit: Month 9 Visit until Month 12 Visit

A subject is considered to have had a recurrence of symptomatic neuroma if all of the following conditions are met:

 Subject experiences a pain level greater than 1 on the 10-point scale of the daily pain diary at least one time during the assessment interval

- The average daily dose of morphine (mg/day) calculated using morphine equivalent dosing during the assessment interval is higher than the average daily dose during the baseline interval (between Screening visit and Operative Day 0)
- VAS pain score is higher at assessment visit than at baseline visit

Adverse Event

An AE is defined as any untoward event (including abnormal lab findings) experienced by a subject (whether or not considered product-related by the site Investigator or Sponsor) after the patient consents to participate in the trial. All AEs that occur during or after study product implantation/device insertion must be recorded in the subject's medical record and reported on the adverse event CRF.

Serious Adverse Events

A serious adverse event (SAE) is any untoward medical occurrence that occurs per the following definition.

- Results in death:
- Is immediately life threatening in the opinion of the site Investigator, the participant was at substantial risk of dying at the time of the event, or use or continued use of the device might have resulted in the death of the subject;
- Requires in-patient hospitalization or prolongation of existing hospitalization.
 Complications that occur during hospitalization are adverse events, and if a complication
 prolongs hospitalization, the event is considered serious. Emergency room visits that do
 not result in overnight hospital admissions should be evaluated for one of the other
 serious outcomes (e.g., life-threatening; required intervention to prevent permanent
 impairment or damage);
- Results in a Congenital Anomaly / Birth Defect suspect that exposure to the device prior to conception or during pregnancy may have resulted in an adverse outcome in the child; or
- Requires Intervention to Prevent Permanent Impairment or Damage medical or surgical
 intervention was necessary to preclude permanent impairment of a body function, or
 prevent permanent damage to a body structure, either situation suspected to be due to the
 use of the device.

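### The SAP's recurrence rule counts worsening beyond the pre-operative state, not return of neuroma pain, and its named test is Month 12 alone, while the protocol endpoint covers the whole 12 months

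*SAP*

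**What the plan says.** The rule is in SAP section 6, under Recurrence of Symptomatic Neuroma: "A subject is considered to have had a recurrence of symptomatic neuroma if all of the following conditions are met". The conditions are:

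- a diary pain score above 1 on the 10-point scale at least once in the assessment interval;
- a mean daily morphine-equivalent dose in that interval that "is higher than the average daily dose during the baseline interval", which runs from Screening to Operative Day 0;
- "VAS pain score is higher at assessment visit than at baseline visit".

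Assessments are at Months 3, 6, 9 and 12. The first interval is "Month 3 Visit: 6 Weeks after Operative Day 0 until Month 3 Visit", and the Month 12 interval covers only the time since the Month 9 visit.

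The reference values are pre-operative. For VAS, "Baseline may be considered to be Day 0 (day of the procedure) or the screening period prior to Day 0". The schedule note in SAP section 5 adds: "In some instances, Visit 1 and Visit 2 can occur on the same day". Entry requires a screening VAS above 65 mm (protocol synopsis) or at least 65 mm (protocol 3.1 and 3.4.2). The scale is bounded: "VAS data are recorded as the number of millimeters from the left of the line with the range 0-100".

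SAP 9.2.1, endpoint 5, names Fisher's exact test on recurrence at Month 12 and notes that visits are judged independently. Protocol 3.5.2 defines the endpoint as the rate over 12 months, and the aim in protocol 2.1 speaks of 3 months.

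**The concern.** Recurrence ordinarily means that pain comes back after relief. This rule asks whether the subject is worse than before surgery on both VAS and opioid dose. Full return of the original pain does not qualify, and no earlier improvement is needed to qualify.

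Protocol 1.1 says opioids control neuroma pain best. That is a reason to look at opioid use, but not to require a dose above the pre-operative one. The SAP itself describes MQS as a measure that "captures non-opioid classes of medications without an equivalency to morphine", so a relapse treated with other drugs fails the rule.

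Prevention of recurrent end-neuroma pain is in the trial title and recurrence is a protocol secondary endpoint. A low count in both arms could be read as successful prevention when the rule has simply not registered relapses. Separately, a Month 12 status and a 12-month cumulative rate are different quantities, and a recurrence at Month 3 can drop out of the named test.

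**Working it through.** The plan gives no recurrence rate, effect size or power for this endpoint, so there is no figure to reproduce.

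**1. The rule applied to cases.** Recurrence = (diary > 1) and (interval MME > baseline MME) and (visit VAS > baseline VAS).

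| Diary | MME, before to interval | VAS, baseline to visit | Counted? |
|---|---|---|---|
| 8 | 20 to 20 | 80 to 80 | No |
| 8 | 20 to 25 | 80 to 79 (after 5 at an earlier visit) | No |
| 8 | 0 to 0 | 80 to 95 | No |
| 8 | 30 to 20 | 80 to 95 | No |
| 10 | 0 to 50 | 100 to 100 | No, and never possible |
| 2 | 20 to 21 | 80 to 81 | Yes |

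Room to worsen is 100 - 65 = 35 mm at the entry threshold and 0 mm at baseline 100. A 1 mm rise is enough in the last row, although protocol 1.1 cites 14-20 mm as the clinically significant difference. None of this needs an assumption.

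**2. How often a relapse meets the VAS condition.** All inputs here are assumed. Screening, Day 0 and relapse VAS are jointly normal with mean 70 or 75, SD 15 or 20 and correlation 0 to 0.9. They are clipped to 0-100, rounded to whole mm, and selected on screening of at least 65.

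- Relapse to the pre-operative distribution: 29-41% with the screening value as baseline, 43-49% with a separate Day 0 value.
- Relapse 10 mm short of it: 4-35%.
- Relapse 10 mm or 20 mm beyond it: 45-89% or 60-96%.
- Adding the opioid condition can only lower these. If it is met in 50% of relapses, with correlation 0 to 0.8 to the VAS condition, the first line becomes 15-35% (screening) or 21-39% (Day 0).

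**3. What lost capture does to the test.** There are 86 / 2 = 43 per arm. Fisher's test needs 6 v 0 events (p = 0.026); 5 v 0 gives p = 0.055. Exact power with equal capture in both arms and no false flags:

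| True rates | 100% captured | 50% | 30% |
|---|---|---|---|
| 30% v 10% | 55% | 21% | 7% |
| 40% v 20% | 45% | 17% | 8% |
| 50% v 20% | 80% | 34% | 17% |

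At 50% capture, 30% v 10% is observed as 15% v 5%; at 30% capture, as 9% v 3%. The ratio stays 3.0 and the difference shrinks from 20 to 10 to 6 points.

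**4. Month 12 against any visit.** For a per-visit rate p, the rate at any of four visits is 1 - (1 - p)^4 if visits are independent. That is 7.8% for p = 2% and 18.5% for p = 5%. With fully correlated visits it stays at p. The two definitions agree only in that limit.

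**The case against.** **Size.** Every input in steps 2 and 3 is assumed. The documents give no relapse distribution, opioid-use share or VAS repeatability, and the VAS condition is met in anything from 4% to 96% of relapses across the scenarios. This stands.

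**Bias.** A reader might infer that the rule distorts the comparison between arms. Nothing in the documents suggests that capture differs by arm, and with equal capture the risk ratio is unchanged.

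**Other coverage.** A reader might also infer that the trial does not measure return of pain. That is not so. The primary VAS endpoint and the secondary AUC, MME and MQS endpoints address pain and medication without this rule. Recurrence is one of six SAP secondary endpoints, and SAP 8.2 disclaims type I error control. This limits the consequence but does not repair the definition.

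**Time frame.** SAP 9.2.1 promises by-visit summaries and a comparative analysis for secondary endpoints, and SAP 9.4 shows no content, so further recurrence analyses may exist out of sight. In the visible text, by-visit summaries do not amount to a cumulative measure and only Month 12 has a named test.

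**Opioid baseline.** When Visits 1 and 2 coincide, one could say that there are no days to average. That goes too far: pain medication is collected at both visits, so an inclusive reading leaves one day. The plan does not say which reading applies.

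**Conclusion.** The point holds on the text. Followed exactly, the rule scores full return of pre-operative pain, and any return without a higher opioid dose than before surgery, as no recurrence. It can never count a subject with baseline 100, and it requires no earlier improvement. It measures worsening beyond the pre-operative state. Its named test at Month 12 does not match the 12-month endpoint in protocol 3.5.2, nor the 3 months in protocol 2.1.

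The amount of under-counting cannot be derived from the documents. If relapse means return to the pre-operative distribution, fewer than half of relapses meet the VAS condition (29-49%); that cap disappears if relapse typically exceeds the pre-operative level. The cost is in power and in the absolute rate. This should be fixed, but it does not touch the other endpoints.

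**What to change.** 1. Remove the requirement that opioid dose exceed the pre-operative dose. Report MME and MQS beside recurrence.
2. Replace the VAS condition with return of pain after improvement. VAS must first be at least 20 mm below baseline at a visit from Month 1 on. At a later visit among Months 3-12 it must then be both at least 20 mm above the lowest such value and within 20 mm of baseline. The 20 mm is the upper end of the protocol's 14-20 mm. Fix one pre-operative baseline VAS, keep the diary condition, and tabulate never-improved subjects separately.
3. Compare arms by Fisher's exact test on recurrence at any of Months 3, 6, 9 or 12. Keep the Month 12 test as supportive, and reconcile protocol 2.1 with 3.5.2.
4. Keep the current composite as a supportive tabulation, labelled as worsening beyond the pre-operative state.

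A rule based on the 20 mm rise alone is suitable only as a sensitivity analysis. In simulation it flags about 82-92% of subjects going from 10 to 30 mm, who remain far better than before surgery.

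**Cost.** SAP wording and programming; the data are already collected. Relapses that stay more than 20 mm below baseline are not counted, missed visits lower the chance of being counted, and VAS error causes some false flags. Simulated with assumed inputs (baseline 70-80, improved level 15 mm, stable subjects at 10-30 mm):

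| Combined rule | Error SD 5-6 | Error SD 10 |
|---|---|---|
| Full relapse detected | 99% or more | about 90-99% |
| Stable subjects flagged | under 1% | 0-6% |

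At SD 10, subjects going from 10 to 30 mm are flagged in 2-6% (1-7% over all baselines and relapse times tried). Never-improved subjects are flagged in 15-19%, which is why they are tabulated apart.

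False flags pull the risk ratio toward 1, which the current rule does not do under equal capture. For true rates of 30% v 10%, 90% detection with 6% false flags gives 0.30 × 0.90 + 0.70 × 0.06 = 0.312 against 0.10 × 0.90 + 0.90 × 0.06 = 0.144, a ratio of 2.2. With 99% and 1% it is 0.304 against 0.108, a ratio of 2.8.

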7.1. Sample Size and Power

A total of 101 participants (15 pilot; 86 comparative/randomized) at up to 20 sites will be enrolled.

7.2. Randomization and Masking

For the comparative study, participants will be centrally randomized 1:1 to one of two treatment groups – neurectomy plus Axoguard Nerve Cap or neurectomy alone – in accordance with a computer-generated randomization schedule to achieve a total of 86 target repairs.

For participants presenting with multiple neuromas during randomization to treatment, multiple neuromas may be included in the study. The primary neuroma will be identified by the investigator prior to randomization. This repair will be utilized for all analyses. Additional (secondary) treated neuromas must meet the same inclusion/exclusion criteria and receive the same treatment (as randomized: Axoguard Nerve Cap or Neurectomy). Whether being treated for

one or multiple neuromas, the acceptability for either treatment shall be decided prior to randomization of the participant.

While blinding the surgeon to treatment is not possible, blinding the participant is possible and all efforts should be taken to preserve this blind. Randomization will be used to assign the participant to a treatment group intra-operatively. Therefore, the participant will be blinded to the treatment used. Direct verbal or written communication regarding treatment identification beyond what is required at an institution for recording the surgical procedures is prohibited.

7.3. Handling of Missing Data and Protocol Violations

Every effort will be made to obtain the VAS pain score data at each scheduled evaluation from all participants who have been randomized, especially at 12 months, since this is the primary efficacy endpoint (PEE). Missing data will be imputed for the primary endpoint only.

All other endpoints will be analyzed with the data available.

No accommodation will be made for a treatment protocol violation unless the proportion of major violations exceeds 5%. In this case, a sensitivity analysis will be done for the primary endpoint only comparing the results when all participants are included, and when those with major protocol violations are excluded. If the results differ, the analysis with the participants included will be the primary analysis.

Major protocol violations include:

- 1. Treating the participant with a non-study treatment or with a study treatment to which the participant was not randomized.
- 2. Assessing an endpoint by a method other than described in the clinical investigational plan (CIP).
- 3. Failing to report a primary endpoint for any reason other than the death of the participant or the participant leaves the study unrelated to the study treatment.

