3.5.2 Efficacy Endpoints

Primary Efficacy Endpoints

- 1. The change in VAS score at 3 months compared to baseline (pilot phase)
- 2. The change in VAS score at 12 months compared to baseline (comparative phase)

Secondary Efficacy Endpoints

- 1. The change in VAS score at 1, 3, 6, 9 and 12 months compared to baseline
- 2. The change in PROMIS® score at 1, 3, 6, 9 and 12 months compared to baseline
- 3. The change in FHSQ score at 1, 3, 6, 9 and 12 months compared to baseline
- 4. Changes in pain medication use at 1, 3, 6, 9 and 12 months compared to baseline
- 5. Rate of recurrence of symptomatic neuroma within 12 months

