5.7.3 Planned Subgroups

5.7.4 Missing Data

Every effort will be made to obtain the required data at each scheduled evaluation from all subjects who have been randomized. In assessing the primary efficacy endpoint, a repeated measures mixed model will be utilized on all observed data.

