7.4.2. Modified Intent-to-Treat Population

For the comparative study, the modified intent-to-treat (mITT) population will be the subset of the ITT population who completed at least one post-baseline assessment of efficacy. Treatment assignment will be based on the treatment as received.

The mITT population will be the primary analysis population for the secondary and tertiary endpoints. It will also be one of the analysis populations for the sensitivity analysis of the primary endpoint by running the analysis with the ITT population and then with the mITT population.

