7.4.3. Per-Protocol Population

For the comparative study, the per-protocol (PP) population will include all participants in the mITT population who have an endpoint for the analysis in question and have experienced no conditions that may confound study outcomes, such as sustaining a foot injury during study follow-up. Treatment assignment will be based on the treatment as received. If there are no participants with confounding events or conditions, this population will not be used.

The PP population will be the analysis population for sensitivity analyses of all endpoints by running the analyses with the primary (default) population (either the ITT or mITT) and then again with the PP.

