9.2. Secondary Efficacy

9.2.1. Endpoints and Analyses

For the comparative study, all secondary endpoints will be summarized by visit with descriptive statistics by treatment group and using a comparative analysis.

	Endpoint	Analysis
1.	The change from baseline of PROMIS Pain Behavior	The treatment groups' scores will be
	Scale score at Month 12	compared with a t-test.
2.	The change from baseline of FHSQ in the General	The treatment groups' scores will be
	Foot Health Scale score at Month 12.	compared with a t-test.
3.	The change from baseline of quantity, quality and	The MME will be compared in the
	class of pain medication use as quantified by MME	treatment groups using a t-test.
	dosing at Month 12.	
4.	The change from baseline of quantity, quality and	The MQS score will be compared in
	class of pain medication use as quantified by the	the treatment groups using a t-test.
	MQS score at Month 12.	
	`	
5.	Recurrence of symptomatic neuroma at Month 12.	Proportion of patients with recurrence
	(Note: Assessments at each visit will be independent.	will be compared between the
	For example, it is possible for a subject to have a	treatment groups using a Fisher's
	recurrence at Month 3 and not have a recurrence at	exact test.
	Month 6.)	

Endpoint	Analysis
6. The Area Under Curve (AUC) of daily pain diary	The AUC will be compared in the
scores and VAS scores during the 12 months	treatment groups using a t-test or other
following the procedure.	appropriate statistical test as
	determined by a biostatistician.

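### Month 12 secondary t-tests use only subjects with a Month 12 score, and the 12-month AUC has no rule for incomplete follow-up; a longitudinal model would remedy both cheaply

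*SAP*

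**What the plan says.** SAP 7.3 treats the primary endpoint and all others differently. For the primary, "Missing data will be imputed for the primary endpoint only"; for the rest, "All other endpoints will be analyzed with the data available".

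SAP 9.2.1 lists six secondary comparisons. Row 1 is "The change from baseline of PROMIS Pain Behavior" score at Month 12 and row 2 is FHSQ General Foot Health at Month 12, each compared by t-test. Rows 3 and 4 (opioid and overall medication scores) also use t-tests, and row 5 (recurrence) uses Fisher's exact test. Row 6 begins "The Area Under Curve (AUC) of daily pain diary" and covers diary and VAS scores over the 12 months after the procedure. It uses a t-test or another test chosen by a biostatistician. No area formula, minimum follow-up or rule for early leavers is shown.

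On populations, "The mITT population will be the primary analysis population for the secondary and tertiary endpoints" (SAP 7.4.2); entry needs one post-baseline efficacy assessment. The per-protocol sensitivity set (SAP 7.4.3) is limited to "participants in the mITT population who have an endpoint for the analysis in question".

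The Protocol has a longitudinal method, but states it for the primary endpoint alone: "In assessing the primary efficacy endpoint, a repeated measures mixed model will be utilized on all observed data" (5.7.4). Its schedule collects PROMIS at screening and all six follow-up visits, and FHSQ at screening and Months 1, 3, 6, 9 and 12.

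**The concern.** A t-test of Month 12 change cannot use a subject who has no Month 12 score. The mITT set nominally includes subjects who left after one visit, but the test drops them, and four or more earlier scores may go unused. The per-protocol analysis cannot reveal the effect, because it too requires an observed endpoint. Leavers are not replaced (Protocol 3.10.2). Precision is lost, and the comparison is biased if leaving is related to outcome in a way that differs between arms.

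The AUC has a separate problem. Lower VAS means less pain, so an area accumulated over a shorter time looks like benefit. If that is how the area is calculated, the arm that loses more subjects gains an advantage unrelated to pain.

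**Working it through.** **Inputs from the documents.** 86 randomized 1:1, so 43 per arm; visits at Week 2 and Months 1, 3, 6, 9 and 12; VAS 0-100 mm with 0 as no pain; entry VAS about 65 mm or more; two-sided alpha 0.05. The plan states no figure on this point that could be reproduced. Dropout rates, PROMIS SD and visit correlations are not given, so those below are assumptions.

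**1. Month 12 t-test against a mixed model.** Assumed: 43 per arm, PROMIS SD 8, 18-26% without Month 12, autoregressive correlation 0.7-0.8 or compound symmetry 0.6, 500 simulated trials per scenario.

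- Same dropout mechanism in both arms: no material bias; t-test variance 1.02-1.15 times that of the mixed model.
- Late, pain-driven dropout in one arm only (autoregressive case): t-test bias 0.57-0.74 T-points.
- Opposite mechanisms in the two arms (autoregressive case): bias 1.01-1.43 T-points, up to 1.43/8 = 0.18 SD.
- Mixed model in the same differential scenarios: 0.01-0.10 T-points.

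A second simulation, on VAS with 10% v 30% dropout driven by pain level, gave almost no bias in change from baseline (0.0 to -0.2 mm), because the subject's own level cancels. The bias therefore depends on how dropout arises.

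**2. AUC for one subject, summed over observed time.** Area = mean pain x months observed.

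- 40 mm for 12 months: 40 x 12 = 480 mm-months.
- 40 mm, leaving at Month 3: 40 x 3 = 120.
- 80 mm, leaving at Month 3: 80 x 3 = 240, half the total of the 40 mm subject followed throughout.

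**3. AUC by arm.** If leavers go half-way on average, the arm mean is mean pain x 12 x (1 - 0.5 x dropout). For 20% v 10% dropout the difference is mean pain x 12 x (0.95 - 0.90):

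- 25 mm: 25 x 12 x 0.05 = 15 mm-months, or 1.25 mm averaged over 12 months.
- 35 mm: 35 x 12 x 0.05 = 21 mm-months, or 1.75 mm.

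In relative terms the higher-dropout arm is 1 - 0.90/0.95 = 5.3% lower, on any pain scale.

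**4. False favourable results.** Simulation with no true effect, 43 per arm, 3,000 trials per scenario; between-subject SD 18 mm, within-subject SD 12 mm; pain flat at 40 mm or falling from 75 to 30 mm; dropout random or pain-driven; trapezoidal area over observed visits. The nominal rate in one direction is 2.5%.

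| Dropout by arm | Mean AUC, higher-dropout arm | Falsely favours that arm |
|---|---|---|
| 10% v 10% | within 0.5% of the other arm | 2.3-3.1% |
| 10% v 20% | 6.1-7.2% lower | 8.2-9.6% |
| 10% v 30% | 11.7-14.5% lower | 19.0-27.6% |

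**5. Two simple alternatives, at 10% v 30%.**

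- *Only subjects with full follow-up:* no bias under random dropout (2.3-2.4% false favourable); under pain-driven dropout, 32-35 mm-months in favour of the higher-dropout arm (8.7-9.5%).
- *Area divided by time observed:* sound if pain is flat, but if pain falls after surgery the higher-dropout arm looks 2.55 mm worse (random) or 1.30 mm worse (pain-driven).

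The reversal can be checked by hand. Let pain fall linearly from 75 to 30 mm over 3 months and then stay flat. The mean to Month 6 is (52.5 x 3 + 30 x 3)/6 = 41.25 mm; the mean to Month 12 is (52.5 x 3 + 30 x 9)/12 = 35.6 mm. A leaver at Month 6 is overstated by 5.6 mm. With 10 percentage points more leavers, the arm looks about 0.6 mm worse. If the fall takes 6 months, the means are 52.5 and 41.25 mm, and the arm looks 1.1 mm worse.

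**The case against.** The strongest reply is that the SAP does not prescribe an unstandardised area. A reader might infer that the AUC will shrink for early leavers, but row 6 speaks of the 12 months and leaves the test open; restricting to subjects with full follow-up is equally compatible. That stands: what the text supports is that the AUC is undefined for incomplete follow-up.

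A reader might also infer that dropout in itself biases the Month 12 t-tests. It does not. Random dropout, or the same mechanism in both arms, leaves no material bias, and subject blinding makes arm-specific mechanisms less likely.

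The Protocol also works to limit missing data. Visit 8 doubles as the early-termination visit, End of Study data are sought before withdrawal (3.4.4.3), and assessments may be returned by phone, mail or electronically (3.10.2). These measures should reduce missingness, but no displayed rule says whether an early-termination score counts as Month 12. Earlier visits are summarized by arm, though only descriptively.

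The consequence is limited. Study success (Protocol 5.10) rests on VAS superiority and safety, and an artefact of 1.25-1.75 mm is small beside the 14-20 mm that the Protocol's background calls clinically significant. That also stands, although the false-positive rates above show that a small shift can matter to a test.

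Finally, Protocol 3.5.2 lists "The change in VAS score at 1, 3, 6, 9 and 12 months compared to baseline", and a reader might infer that the SAP has no between-arm analysis of the separate visits. That cannot be asserted: SAP 9.4 is a bare heading in this copy, and its content may have been removed.

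**Conclusion.** The concern holds as a cheap improvement to the secondary analyses. Rows 1 and 2 discard collected data, at a cost of about 2-15% in variance under the assumed 18-26% missingness. Bias of 0.6-1.4 T-points appears only if outcome-related dropout differs between arms. Row 6 needs a definition. Summed over observed time, the AUC would favour the arm with more dropout by about 15-21 mm-months at an assumed 20% v 10% leaving half-way with mean pain of 25-35 mm; with equal dropout it would not. Restricting to full follow-up avoids the shrinkage but is biased when dropout follows pain.

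Every size here rests on assumed dropout rates, SDs and correlations. The primary endpoint is not affected by this rule. Rows 3 to 5 fall under the same rule, but were not examined in these calculations.

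**What to change.** In SAP 7.3 and 9.2.1:

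1. Analyse PROMIS Pain Behavior and FHSQ General Foot Health with the repeated-measures mixed model of Protocol 5.7.4 (treatment, visit, treatment-by-visit) on all observed visits, and report the Month 12 contrast.
2. Derive the 12-month VAS AUC contrast as a linear combination of visit means from the VAS mixed model. Taking Week 2 as 0.5 months, the trapezoidal weights at baseline, Week 2 and Months 1, 3, 6, 9 and 12 are 0.25, 0.5, 1.25, 2.5, 3, 3 and 1.5, which sum to 12.
3. Derive the diary AUC in the same way from a longitudinal model, for example of weekly or monthly diary means, or by multiple imputation. Do not divide by days observed: with pain falling after surgery, that counts against the arm with more dropout.
4. Keep the available-case t-tests as sensitivity analyses.

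The cost is SAP wording, some programming, a covariance assumption and reliance on data missing at random. No new data or subjects are needed.
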